9.3 Analysis Populations

9.3.1 Intention-to-Treat Analysis Set

All subjects who are randomized regardless of treatment adherence or availability of follow-up data will be included in the intention-to-treat analysis set (ITT). All analyses of the ITT will be based on each subject's randomized assigned treatment.

9.3.2 Safety Analysis Set

All subjects who are randomized and take at least one dose of double-blind study medication will be included in the Safety Analysis Set. Safety analyses will be based on the medication that was actually dispensed to each subject. This is the primary analysis set for safety. If a randomization error causes a subject in the placebo arm to receive active drug inadvertently, the subject will be considered exposed to active drug and will be analyzed accordingly in the SAS population. If a subject in the active arm receives placebo inadvertently but receives active drug subsequently, the subject will be considered exposed to active drug and will be analyzed accordingly.

9.3.3 Per Protocol Analysis Set

The Per Protocol (PP) Analysis Set will include all subjects in the FAS who meet the study eligibility requirements and have no major protocol deviations that will affect the validity of the efficacy measurements. Protocol deviations that may result in subject exclusion from the PP Analysis Set will be detailed in the Statistical Analysis Plan. The subject assignment to the PP Analysis Set will be determined prior to database lock.

9.4 Demographics and Baseline Characteristics

Demographic characteristics include age, gender, race, ethnicity, country, and CV history. Baseline characteristics include baseline HbA1c value, blood pressure (systolic and diastolic), body weight, fasting plasma glucose level, and stratification factors determined at screening visit, including HbA1c ($< 9.5\%$ or $\geq 9.5\%$), eGFR (< 60 or ≥ 60 mL/min/1.73 m²), body mass index (BMI < 25 kg/m² or ≥ 25 kg/m²) and history of heart failure (yes or no). Summary statistics by treatment group will include counts and percentages for discrete variables, and means, SD, Q1, medians, Q3, minimum and maximum for continuous variables and counts and percentage of patients for categorical variables. A further descriptive summaries will be provided separately for subjects who enrolled prior to and subjects who enrolled post the modification of inclusion criteria.

9.5 Primary Endpoints

9.5.1 Primary Efficacy Endpoint

The primary efficacy hypothesis is that bexagliflozin reduces HbA1c after 24 weeks of treatment when compared to placebo. The primary efficacy analysis on change in HbA1c at week 24 is based on the ITT using all observed data. Missing data will be handled using a mixed model repeated measures (MMRM) approach and will include terms for visit, treatment, treatment-by-visit interaction and randomization stratification factors as fixed effects and the corresponding baseline HbA1c value as a fixed effect covariate. Least squares mean treatment differences between the bexagliflozin group and the placebo group will be estimated from the model at week 24 with the corresponding p-values and their two-sided 95% CIs presented. An unstructured covariance will be used to model the within-subject correlation. In the unlikely event the model with the unstructured covariance structure does

not converge, an autoregressive (1) covariance structure will be used. HbA1c values obtained after the start of rescue medication will not be excluded from the analysis.

As a secondary sensitivity analysis, the multiple imputation method will be used to impute missing observations (including observations obtained after rescue medication) prior to carrying out the MMRM analysis. To further examine the sensitivity of the analysis, a last observation carried forward (LOCF) method will then be used to impute the missing observations prior to carrying out the MMRM model.

For supportive analyses, the primary efficacy endpoint will be analyzed with observed available data using the PP analysis sets in a similar manner as above.

9.5.2 Handling Dropouts, and Missing Data

Discontinuation criteria are explained in [Section 6.13](#). Subjects who withdraw consent to participate in the study will not be replaced.

The early termination rate is estimated to be 6.5% annually. To the extent possible, attempts will be made to minimize the amount of missing data through measures planned in the study conduct. But if data are missing for the primary endpoint and the first key secondary endpoint (ie, change of HbA1c for subjects who have been prescribed insulin), they will be handled as follows:

1. All observed data will be analyzed and data obtained after rescue will not be excluded and considered as missing. This will be considered the primary analysis.
2. Missing primary efficacy endpoint information will be imputed via multiple imputation linear regression approach. A total of 10 imputed datasets will be generated, and the corresponding primary analyses will be carried out on each imputed dataset for each endpoint; the analyses results will be combined across the 10 datasets using the standard techniques for multiply imputed data sets in order to yield overall treatment comparison results on the imputed data for each endpoint.

The number, timing, pattern, reason for and possible implications of missing values in efficacy assessments will be investigated. The dropout patterns will be assessed by Kaplan-Meier plots if applicable to assess whether they differ between treatment groups.

The handling of missing safety endpoint (MACE+) data is described below in section 9.6.3; however, analyses on MACE+, while being collected in C-476, will only be formally analyzed in the meta-analysis.

For all other endpoints, the missing data will not be imputed and only the observed data will be used in the analyses.

9.5.3 Multiple Comparisons / Multiplicity

A sequential testing procedure will be applied to the testing of the treatment differences of the primary and key secondary efficacy endpoints, to control the familywise error rate at a two-sided 5% level. Each comparison will be done based on the pre-specified testing hierarchy, so multiplicity adjustment will not be performed.

9.6 Secondary Endpoints

9.6.1 Key Secondary Efficacy Endpoints

The key secondary efficacy endpoints include:

- Change in HbA1c from baseline to week 24 in randomized subjects who have been prescribed insulin to control their diabetes
- Change in body weight from baseline to week 48 in subjects with a BMI ≥ 25 kg/m²
- Change in SBP from baseline to week 24 in subjects with baseline systolic blood pressure ≥ 140 mmHg

It is anticipated that approximately 50% of the randomized subjects will have been prescribed insulin to manage their disease. The sample size for the key secondary efficacy end point to evaluate the treatment effect of bexagliflozin compared to placebo on the change in HbA1c from baseline to week 24 in subjects who have been prescribed insulin to control their diabetes is estimated to be 800. For this key secondary endpoint, the estimated sample size will yield >90% power to detect a treatment effect of 0.3% assuming the SD is 1.1% for a two-sided superiority testing.

It is also anticipated that a high proportion of the randomized subjects would have a baseline BMI ≥ 25 kg/m² and baseline SBP ≥ 140 mmHg in this cardiovascular risk enriched population for the analysis in change in body weight and change in SBP.

A hierarchical testing procedure will be applied to these endpoints in the sequence provided above. These key secondary endpoints will only be tested sequentially when significant treatment differences are established for the primary efficacy endpoint in the comparisons between bexagliflozin and placebo.

The comparison between treatment populations at week 24 (HbA1c and SBP) or 48 (body weight) will be carried out using an MMRM ANCOVA model with unstructured covariance assumption. The model will include terms for treatment, randomization stratification factors, visit, and treatment-by-visit interaction as fixed effects and the corresponding baseline value as an additional fixed effect covariate. Treatment comparison p-values and the difference at week 24 (HbA1c and SBP) or 48 (body weight) will be estimated from the model, with the two-sided 95 % CIs of the difference also presented. If the model does not converge with the unstructured correlation assumption, an autoregressive (1) covariance structure will be used.

9.6.2 Exploratory Efficacy Endpoints

The exploratory secondary efficacy endpoints include:

- Change from baseline in HbA1c over time
- Change from baseline in FPG over time
- Change from baseline in body weight over time
- Change from baseline in SBP over time
- Requirement of additional anti-diabetic medications, including insulin; and time to first use of additional anti-diabetic medication
- Requirement of reduced anti-diabetic medications, including insulin dose over time
- Hospitalization for heart failure in all subjects and in subjects with a history of heart failure
- time to hospitalization for heart failure in subjects in all subjects and in subjects with a history of heart failure

For changes from baseline in HbA1c, FPG, body weight, and SBP over time, a similar MMRM ANCOVA model will be used as for the key secondary efficacy endpoints. Of interest in the MMRM ANCOVA model is the difference between treatments on these endpoints across all post-baseline time points. Also, changes from baseline for each endpoint will be estimated and analyzed at each study visit using this MMRM model. Specifically, for each endpoint, treatment difference in least squares means will be estimated by visit from the model with the corresponding p-values and the two-sided 95% CIs of the difference between treatments.

Endpoints measuring proportions over time will be analyzed using generalized estimating equation (GEE) logistic regression using similar independent variables as the MMRM ANCOVA models above (the treatment-by-visit interaction term will be removed if not significant), and using an unstructured correlation structure (or autoregressive(1) if the model with the unstructured structure does not converge). Of interest is the difference between treatments across all post-baseline time points. Also, odds ratios will be estimated from the model with the corresponding p-values and their two-sided 95% CIs presented at each visit. For time-to-event endpoints, Cox proportional hazards models with treatment and randomization stratification factors as the covariates will be used to estimate the hazard ratio of the endpoint, p-value and its two-sided 95% confidence interval comparing bexagliflozin to placebo. Subjects who withdraw from the trial and for whom no follow up event data are collected (i.e., lost to follow-up subjects) will be censored at the last known follow-up.

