7.4 Exit Visit

7.4.1 Visit FU (4 weeks after the last dose of investigational product is administered or if a subject withdraws consent)

- Review SMBG and glycemic control record
- Perform a complete physical examination
- Measure vital signs, including blood pressures and heart rate
- Measure body weight
- Perform 12-lead ECG if clinically indicated
- Draw blood from subjects who have completed a compliant fast as described in [Section 6.7.2.1](#). The specific laboratory tests scheduled for this visit are listed in [Appendix 2](#)
- Collect a clean-catch, mid-stream urine sample for urinalysis in all subjects and for UPT for women of child bearing potential
- Assess AEs, potential DKA, and record concomitant medications: If a subject has an ongoing SAE, the subject will be followed until the AE has resolved or no meaningful further improvement can be expected. Every possible attempt should be made to document resolution of acute and chronic toxicities.

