6.4. ANALYSIS VISIT WINDOWS

Table 6 shows how data will be mapped to visit number prior to selection of records for analysis. All post-baseline visits, including unscheduled and early termination visits, will be mapped.

After mapping the data to the visits, the following rules will apply unless other handling is specified for a particular analysis.

- If multiple records are available within a single visit window, the record closest to the planned assessment day will be selected for analysis.
- If 2 records are equidistant from the target day, then the later record will be selected.
- If a subject has no record in an analysis window, the data will be considered missing at that visit.

Table 6 Analysis Visit Windows

Study Day Window	Scheduled day	Scheduled Visit/Week
Day 1 - 63	Day 42	Visit 5/Week 6
Day 64 - 105	Day 84	Visit 6/Week 12
Day 106 - 147	Day 126	Visit 7/Week 18
Day 148 - 210	Day 168	Visit 8/Week 24
Day 211 - 294	Day 252	Visit 9/Week 36
Day 295 - 420	Day 336	Visit 10/Week 48
Day (xx*7-83) - minimum (xx*7+84, End of Treatment Visit date)	Day (xx*7)	Visit /Week xx, where xx is every 24 weeks.
> End of Treatment Visit date + 7	End of Treatment Visit + 28	Follow-up Visit

If there are multiple end of treatment visits, the one closest to the last dose date will be used. If multiple records are equidistant from the last dose date, the later one will be used. Analysis visit windows will be used for all lab, vital sign, and ECG data.

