8.2.2.2. Changes from baseline in HbA_{1c} and FPG over time

Of interest is the difference between treatments on these two endpoints across all post-baseline time points with sufficient number of values. If for any treatment arm, less than 20 subjects completed the assessment in the analysis visit window, the visit will not be included in the analysis. Both endpoints will be analyzed using MMRM model with the change from baseline values across all post-baseline visits used as dependent variable. The fixed effect will include baseline eGFR (≥ 60 or < 60 mL min⁻¹ [1.73m]⁻²), baseline BMI ($<$ or ≥ 25 kg m⁻²), and history of heart failure (yes or no), insulin use or not, treatment, visit, treatment and visit interaction, other hypoglycemic agent use (no change, after relaxation, or after intensification), treatment and other hypoglycemic agent use interaction, and baseline value. For each endpoint, treatment difference in least squares means will be estimated by visit from the model with the corresponding p-values and the two-sided 95% CIs of the difference between treatments.

Analysis of HbA_{1c} over time will also be conducted for subjects who have been prescribed insulin or sulfonylurea to control their diabetes.

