8.2.2.3. Changes from baseline in SBP and weight over time

Both endpoints will be analyzed using MMRM model with the change from baseline values across all post-baseline visits used as dependent variable. The fixed effect will include baseline eGFR (≥ 60 or < 60 mL min⁻¹ [1.73m]⁻²), baseline BMI ($<$ or ≥ 25 kg m⁻²), and history of heart failure (yes or no), insulin use or not, treatment, visit, treatment and visit interaction, and baseline value. For each endpoint, treatment difference in least squares means will be estimated by visit from the model with the corresponding p-values and the two-sided 95% CIs of the difference between treatments.

8.2.2.4. Proportions of subjects with intensification and relaxation of hypoglycemic agent (i.e. requirement of additional anti-diabetic medications and with requirement of reduced anti-diabetic medications)

These endpoints will be analyzed using logistic regression. The model will include terms for treatment, region, baseline eGFR categories (<60 or ≥ 60 mL min⁻¹ per 1.73 m²), baseline BMI ($<$ or ≥ 25 kg m⁻²), and history of heart failure (yes or no), insulin use or not,

and baseline HbA_{1c}. The LS mean proportions and the two-sided 95% CI for each treatment will be presented. Also, odds ratio of treatment difference of bexagliflozin group over the placebo group will be estimated from the model with the corresponding p-values and their two-sided 95% CIs presented. Analysis will also be conducted for subjects who have been prescribed insulin or sulfonylurea to control their diabetes.

8.2.2.5. Proportions of subjects with hospitalization of heart failure in all subjects, with hospitalization of heart failure in subjects with a history of heart failure

These endpoints will be analyzed using logistic regression. The model will include terms for treatment, region, baseline eGFR categories (<60 or ≥60 mL min⁻¹ per 1.73 m²), baseline BMI (< or ≥25 kg m⁻²), history of heart failure (yes or no), insulin use or not, and baseline HbA_{1c}. Odds ratios will be estimated from the model with the corresponding p-values and their two-sided 95% CIs. The odds ratios of bexagliflozin group over the placebo group will be estimated from LS means based on the model with the corresponding p-values and their two-sided 95 % CIs presented.

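### The exploratory over-time models for HbA1c, FPG, weight and SBP do not exclude the off-drug Follow-up visit, so the across-visit difference named as of interest would mix treatment effect with washout

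*Combined protocol and SAP*

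**What the plan says.** **Quantity of interest.** Protocol 9.6.2, covering HbA1c, FPG, body weight and SBP over time: "Of interest in the MMRM ANCOVA model is the difference between treatments on these endpoints across all post-baseline time points". It then adds analyses at each visit: "treatment difference in least squares means will be estimated by visit from the model". SAP 8.2.2.2, for HbA1c and FPG: "Of interest is the difference between treatments on these two endpoints across all post-baseline time points with sufficient number of values". SAP 8.2.2.3 (SBP and weight) has no such sentence.

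**Data in the model.** SAP 8.2.2.2 and 8.2.2.3 both have "change from baseline values across all post-baseline visits used as dependent variable". The only rule that drops a visit applies to HbA1c and FPG, when in any arm "less than 20 subjects completed the assessment in the analysis visit window". SBP and weight have no such rule.

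**Visit mapping.** SAP 6.4: "All post-baseline visits, including unscheduled and early termination visits, will be mapped". Table 6 in that section gives the Follow-up Visit its own row, with target day End of Treatment + 28, and applies the windows to all lab and vital-sign data.

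**The Follow-up visit.** Protocol 7.4.1 heads it "Visit FU (4 weeks after the last dose of investigational product is administered". Weight, blood pressure and a fasting blood draw are scheduled there, and protocol Appendix 2 marks HbA1c and FPG at that visit.

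**Model terms.** Protocol 9.6.2 borrows the key secondary model of 9.6.1: "The model will include terms for treatment, randomization stratification factors, visit, and treatment-by-visit interaction as fixed effects". The SAP over-time models keep the treatment-by-visit interaction. For HbA1c and FPG, SAP 8.2.2.2 adds other hypoglycemic agent use and its interaction with treatment.

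**The concern.** The objective in protocol 2.2 is the effect of bexagliflozin treatment on these measures over time. At the Follow-up visit subjects are off study drug by design, so its between-arm difference measures how much effect persists about 4 weeks after stopping. Nothing in 9.6.2, 8.2.2.2 or 8.2.2.3 leaves this visit out, and with about 1650 subjects randomized it would readily pass the 20-subject rule.

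Elsewhere the SAP does bound its visits. Section 8.1.1 describes comparisons at each visit and over weeks 6 to 24, 8.2.1.1 uses data up to week 24, and 8.2.1.3 uses visits up to week 24. The over-time sections have no such limit.

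At stake is the meaning of any single over-time figure. There is also room to choose, after unblinding, whether Follow-up counts.

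**Working it through.** The plan gives no numerical target for these analyses, so there is no figure to reproduce. Three checks follow.

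**1. Size of the effect on an across-visit average**

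Inputs:
- Treatment-period visits that measure the endpoints (protocol Appendices 1 and 2): weeks 6, 12, 24, 36, 48, 72 and 96 for about 104 weeks of treatment, so k = 7. Adding weeks 120 and 144 for about 156 weeks gives k = 9. The 104 to 156 week range is in the Appendix 1 footnote.
- Weighting of visits: not given; equal weights assumed.
- Fraction r of the effect remaining at Follow-up: not given; 0 to 1 shown.

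With a constant on-drug effect, average ÷ on-drug effect = (k + r)/(k + 1), so understatement = (1 − r)/(k + 1).

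| k | r = 0 | r = 0.5 | r = 1 |
|---|---|---|---|
| 7 | 1/8 = 12.5% | 0.5/8 = 6.25% | 0% |
| 9 | 1/10 = 10.0% | 0.5/10 = 5.0% | 0% |

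To illustrate, take the 0.79% HbA1c difference that protocol 3.3.2 quotes from an earlier study. At r = 0 it becomes 0.79 × 7/8 = 0.69 or 0.79 × 9/10 = 0.71. At r = 0.5 it becomes 0.74 or 0.75. Protocol 6.14 says HbA1c reflects 2 to 3 months of glycemia, so r = 0 is unlikely for HbA1c at 4 weeks. One further 24-weekly visit (k = 10) would lower the r = 0 figure to 1/11 = 9.1%.

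**2. By-visit differences without a shared agent-use term (the form for SBP and weight)**

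An MMRM with treatment, visit, treatment-by-visit, baseline and unstructured covariance was simulated: 1100 v 550 subjects, k = 7, effect −0.79, SD 1.1, correlation 0.6 (assumed), r = 0, complete data. It was fitted with and without Follow-up in three simulated trials.
- On-treatment by-visit differences changed by at most 0.0002.
- The simple average over visits moved from −0.806 to −0.702, from −0.774 to −0.683, and from −0.744 to −0.645. These are reductions of 12.9%, 11.8% and 13.3%, in line with the 12.5% above.

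**3. By-visit differences with the shared term (HbA1c and FPG)**

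SAP 8.2.2.2 has one treatment-by-agent-use coefficient, β, for all visits. If agent use modifies the effect on drug but there is no effect left to modify at Follow-up, including that visit pulls β toward zero. The by-visit LS-mean difference weights agent-use categories by some w, while the data at a visit fix the difference at the observed proportion p. So, approximately, shift = (w − p) × change in β.

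A simulation with an effect of −0.79, reduced to −0.40 after intensification, and 0 at Follow-up (all assumed) moved β from 0.40 to 0.30. The on-treatment LS-mean difference at equal category weights moved from −0.646 to −0.667, so 0.021/0.646 = 3% away from zero. Another set of assumed intensification rates gave about 5%. Swapping the two assumed effects, so that β is negative, moved the estimate toward zero by a similar few percent. This matches the formula, where the sign depends on β and on whether w exceeds p.

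The covariate cannot absorb therapy added between last dose and Follow-up, because SAP 6.2.7 does not count increases after the last day of investigational product as intensification.

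**The case against.** The strongest reply is that the output actually specified is by visit. Both SAP sections ask for LS-mean differences by visit from a model with treatment-by-visit interaction. Table 6 gives Follow-up its own level and caps the post-week-48 windows at the End of Treatment visit date. Follow-up therefore gets its own estimate and is not averaged into the on-drug visits. No pooled contrast, weighting or output table is defined, and protocol 9.1 makes the separate analysis plan the final one. The endpoints are exploratory, with nominal p-values (SAP 8.2.2).

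Most of this stands. A reader might infer that every reported over-time difference is diluted toward zero. The documents do not support that: for SBP and weight the on-treatment by-visit estimates hardly move, and for HbA1c and FPG the shift can go either way. Nor can the 10.0 to 12.5% be read as a property of the plan, since it needs equal weights and complete loss of effect.

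The reply does not dispose of the point. Protocol 9.6.2 names the across-visit difference first and introduces the by-visit analysis as an addition, and SAP 8.2.2.2 repeats the across-visit interest. SAP 8.1.1 shows that an across-visit comparison is read from this kind of model, and there it is confined to weeks 6 to 24. The shared agent-use coefficient also means that the interaction does not fully insulate the HbA1c and FPG estimates.

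**Conclusion.** The point holds in limited form. Followed literally, the plan puts a planned washout visit into the over-time models and into the across-visit difference that protocol 9.6.2 (all four endpoints) and SAP 8.2.2.2 (HbA1c and FPG) name as of interest.

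- **Across-visit difference:** understated by up to 10.0 to 12.5% with 7 to 9 treatment-period visits, or 5.0 to 6.3% if half the effect remains. HbA1c should sit below the upper figures because of its memory. This rests on equal weights and an assumed retained effect.
- **By-visit, SBP and weight:** essentially unaffected. The simulation used complete data; dropout could add a small shift through the covariance.
- **By-visit, HbA1c and FPG:** a shift of a few percent in either direction, under assumed effect modification and intensification rates.
- **Primary and key secondary analyses:** unaffected; their contrasts are taken at week 24 or week 48.

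This is worth correcting because the remedy is so small. It does not threaten the trial's confirmatory conclusions.

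**What to change.** In SAP 8.2.2.2 and 8.2.2.3, and in protocol 9.6.2, replace the reference to all post-baseline visits or time points with treatment-period visits from week 6 through End of Treatment, excluding the Follow-up Visit. Apply the same limit to any across-visit contrast, and state its visit weights or say that none will be reported. Summarise the Follow-up Visit separately by arm as an off-drug time point. If the protocol is not amended, record the change in SAP section 12.

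The cost is a sentence or two of wording and a visit filter in the programs. No new data are needed.
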